8.0 TOXICITIES TO BE MONITORED AND DOSE MODIFICATIONS

8.1 NCI Common Terminology Criteria for Adverse Events

This study will utilize the CTCAE (NCI Common Terminology Criteria for Adverse Events) Version 5.0 for toxicity and Serious Adverse Event reporting. A copy of the CTCAE Version 5.0 can be downloaded from the CTEP home page (<http://ctep.cancer.gov>). All appropriate treatment areas should have access to a copy of the CTCAE Version 5.0.

8.2 Dose Modifications

General Considerations:

For a more comprehensive list of managing toxicities or management see package insert. Treatment and dose modifications are at the discretion of the treating investigator.

Unacceptable (Grade 3 or greater) and related toxicity necessitating removal from protocol treatment is expected to be rare. Cause of all \geq Grade 3 toxicity should be investigated and changes to protocol treatment made only if toxicity deemed to be related (definite, probable or possible). Antiviral should not be stopped as withdrawal of antiviral may precipitate flare of hepatitis. Instead, patient should be switched to another antiviral that is not associated with that toxicity.

Acute kidney injury has only been reported for TDF. If deemed to be related to TDF, then stop TDF and switch to TAF or ETV.

Lactic acidosis is considered a class effect although data associating it with TDF or TAF are lacking. If deemed to be related, then stop the drug, monitor closely, and when resolved, switch to an alternate antiviral. (48)

Exacerbation of hepatitis associated with discontinuation of antiviral is not related to the antiviral drug itself. This is not applicable to this oncology population where antiviral therapy discontinuation is not expected during anticancer therapy.

TAF-treated patients:

No dosage adjustment of tenofovir alafenamide (TAF) is required in patients with renal impairment with a creatinine clearance ≥ 15 mL/min. Patients with a creatinine clearance < 15 mL/min who are receiving hemodialysis may take the usual dose of TAF (25 mg) on days of dialysis after completion of hemodialysis treatment. TAF is not recommended for patients with creatinine clearance < 15 mL/min who are not receiving hemodialysis.

If a study patient develops creatinine clearance below 15 mL/minute during study participation and is not receiving hemodialysis, then TAF will be discontinued with substitution with an appropriate alternative antiviral as described below at the discretion of the investigator.

TDF-treated patients:

The following guidelines should be used for dose modification of TDF based on creatinine clearance.

Creatinine clearance (mL/min)	Dose
≥ 50	300 mg daily
30-49	300 mg every 48 hours
10-29	300 mg every 72 to 96 hours
Hemodialysis	300 mg every 7 days

ETV-treated patients:

The following guidelines should be used for dose modification of ETV based on creatinine clearance.

Creatinine clearance(mL/min)	Dose
>50	0.5 mg daily
30-50	0.25 mg daily or 0.5 mg every 48 hours
10-30	0.15 mg daily or 0.5 mg every 72 hours
<10 or hemodialysis or peritoneal dialysis	0.05 mg daily or 0.5 mg every 7 days

Dose Modification Contacts

For treatment or dose modification questions, please contact [name]., M.P.H., [contact], E-mail: [contact] or [name]., [contact] or E-mail: [contact].

8.3 Adverse Event Reporting

Toxicities (including suspected reactions) that meet the expedited reporting criteria as outlined in [Section 16.0](#) of the protocol must be reported to the Operations Office, Study Chair and NCI via CTEP-AERS, and to the IRB per local IRB requirements.

9.0 STUDY CALENDAR

9.1 ARM 1: Prophylactic anti-HBV therapy Arm (HBsAg+ Patients)

REQUIRED STUDIES	Week 0 (Registration)	Weeks from Registration (± 2 weeks unless otherwise specified)							Follow-Up after Off HBV Treatment (Every 8 Weeks Through Week 104) Every 8 Weeks from Week 32 through Week 104 (24 months)	at HBV Reactivation	
		4	8	12	16	20	24				
PHYSICAL											
History and Physical Exam	X										
HBV Assessment ^(F)	X	X	X	X	X	X	X	X	X	X	
Toxicity Notation ^(F)		X	X	X	X	X	X	X			
Review Intake Calendar ^(F)		X	X	X	X	X	X	X			
LABORATORY											
Serum creatinine/Creatinine Clearance	X	X	X	X	X	X	X	X			
Total Bilirubin	X	X	X	X	X	X	X	X	X		
Direct Bilirubin ^{(A) (E)}	X	X	X	X	X	X	X	X	X		
ALT	X	X	X	X	X	X	X	X	X		
International Normalized Ratio (INR) ^(A)	X	X	X	X	X	X	X	X	X		
Complete Blood Count (CBC)	X										
HBV DNA ^(B)	X	X	X	X	X	X	X	X	X		
IgM anti-HAV ^{(B) (E)}	X	X	X	X	X	X	X	X	X		
anti-HCV ^{(B) (E)} or HCV RNA ^{(B) (E)}		X	X	X	X	X	X	X	X		
HBeAg ^(B)	X	X	X	X	X	X	X	X	X		

Calendar 9.1 continued on next page. Click here for [Footnotes](#)

REQUIRED STUDIES	Week 0 (Registration)	Weeks from Registration (± 2 weeks unless otherwise specified)							Follow-Up after Off HBV Treatment (Every 8 Weeks Through Week 104) (24 months)	at HBV Reactivation
		4	8	12	16	20	24			
SPECIMEN SUBMISSION ^(C)										
Serum (10 ml blood in red top tube)	X		X		X		X	X		X
Whole blood (50 ml in EDTA tubes)	X			X			X			X
TREATMENT										
Arm 1- Prophylactic Anti-HBV Therapy ^(D)	X	X	X	X	X	X	X	X		

NOTE: Forms are found on the protocol abstract page on the SWOG website (www.swog.org). Forms submission guidelines are found in [Section 14.0](#). Click here for [Footnotes](#).

NOTE: Unless indicated otherwise in the protocol, scheduled procedures and assessments (treatment administration, toxicity assessment for continuous treatment, disease assessment, specimen collection and follow-up activities) must follow the established SWOG guidelines as outlined in SWOG Best Practices, <https://www.swog.org/clinical-trials/protocol-workbench>.

FOOTNOTES:

- (A) If total bilirubin > 3 mg/dL, or if ALT > 5 x IULN or > 200 U/L, per usual care (see [Section 7.4](#)).
- (B) If hepatitis flare (defined as ALT > 3 x baseline and > 100 U/L).
- (C) See [Sections 15.0](#) and [Appendix 18.1](#).
- (D) See [Section 7.2a](#).
- (E) To be ordered the same day (or within 7 days) if hepatitis flare occurs.
- (F) See [Section 7.1b](#).

Allowable Windows

All visits and procedures must occur within ± 2 weeks of target date (based on date of registration), unless otherwise specified.

9.2 ARM 2 & ARM 3: Upon Indication Arms (HBsAg+ or HBsAg- Patients)

REQUIRED STUDIES	Week 0 (Registration)	Weeks from Registration (± 2 weeks unless otherwise specified)						Follow-Up after Off HBV Treatment (Every 8 Weeks Through Week 104 (24 months)	at HBV Reactivation
		4	8	12	16	20	24		
PHYSICAL									
History and Physical Exam	X								
HBV Assessment ^(H)	X	X	X	X	X	X	X	X	X
Toxicity Notation ^{(G) (H)}		X	X	X	X	X	X	X	
Review Intake Calendar ^{(G) (H)}		X	X	X	X	X	X	X	
LABORATORY									
Serum creatinine/Creatinine Clearance	X	X	X	X	X	X	X	X	
Total Bilirubin	X	X	X	X	X	X	X	X	
Direct Bilirubin ^{(A) (F)}									
ALT	X	X	X	X	X	X	X	X	
International Normalized Ratio(INR) ^(A)	X	X	X	X	X	X	X	X	
Complete Blood Count	X								
HBV DNA ^{(B) (C) (F)}	X	X	X	X	X	X	X	X	
HBsAg ^(C)	Not Indicated in Arm 2*								
IgM anti-HAV ^{(B) (C) (F)}	X	X	X	X	X	X	X	X	
anti-HCV ^{(B) (C) (F)} or HCV RNA ^{(B) (C) (F)}		X	X	X	X	X	X	X	
Anti-HBs (Arm 3) ^{(B) (C) (F)}	X	X	X	X	X	X	X	X	
HBeAg (if become HBsAg+) ^{(B) (C) (F)}	X	X	X	X	X	X	X	X	

REQUIRED STUDIES	Week 0 (Registration)	Weeks from Registration (± 2 weeks unless otherwise specified)							Follow-Up after Off HBV Treatment (Every 8 Weeks Through Week 104 (24 months)	at HBV Reactivation
		4	8	12	16	20	24			
SPECIMEN SUBMISSION ^(D)										
Serum (10 ml blood in red top tube)	X		X		X		X	X		X
Whole blood (50 ml in EDTA tubes)	X			X			X			X
TREATMENT										
Upon-Indication anti-HBV therapy ^(E)	X	X	X	X	X	X	X	X		

NOTE: Forms are found on the protocol abstract page on the SWOG website (www.swog.org). Forms submission guidelines are found in [Section 14.0](#).

NOTE: Unless indicated otherwise in the protocol, scheduled procedures and assessments (treatment administration, toxicity assessment for continuous treatment, disease assessment, specimen collection and follow-up activities) must follow the established SWOG guidelines as outlined in SWOG Best Practices, <https://www.swog.org/clinical-trials/protocol-workbench>.

FOOTNOTES for Calendar 9.2:

- (A) If total bilirubin > 3 mg/dL, or if ALT > 5x IULN or > 200 U/L, per usual care (see [Section 7.4](#)).
- (B) If hepatitis flare (defined as ALT > 3 x baseline and > 100 U/L) if patient is HBsAg-positive.
- (C) If hepatitis flare (defined as ALT > 3 x baseline and > 100 U/L) in patient with baseline HBsAg-negative.
- (D) See [Sections 15.0](#) and [Appendix 18.1](#).
- (E) See [Section 7.0](#)

(F) To be ordered the same day (or within 7 days) if hepatitis flare occurs.

(G) If patient initiated anti-viral treatment per protocol.

(H) See [Section 7.1b](#).

Allowable Windows

All visits and procedures must occur within ± 2 weeks of target date (based on date of registration), unless otherwise specified.

9.3 ARM 4: Usual Care Arm (HBsAg- Patients)

REQUIRED STUDIES	Week 0 (Registration)	Weeks from Registration (± 2 weeks unless otherwise specified)							Follow-Up after Off HBV Treatment (Every 8 Weeks Through Week 104 (24 months)	at HBV Reactivation
		4	8	12	16	20	24	Every 8 Weeks from Week 32 through Week 104 (24 months)		
PHYSICAL										
History and Physical Exam	X									
HBV Assessment (H)	X	X	X	X	X	X	X	X	X	X
Toxicity Notation (G) (H)		X	X	X	X	X	X	X		
Review Intake Calendar (G) (H)		X	X	X	X	X	X	X		
LABORATORY										
Serum creatinine/Creatinine Clearance	X	X	X	X	X	X	X	X		
Total Bilirubin	X	X	X	X	X	X	X	X	X	
Direct Bilirubin (A) (F)	X	X	X	X	X	X	X	X	X	
ALT	X	X	X	X	X	X	X	X	X	
International Normalized Ratio (INR) (A)		X	X	X	X	X	X	X	X	
Complete Blood Count (CBC)	X									
HBV DNA (B) (C) (F)	X	X	X	X	X	X	X	X	X	
HBsAg (B) (C) (F)	X	X	X	X	X	X	X	X	X	
IgM anti-HAV (B) (C) (F)	X	X	X	X	X	X	X	X	X	
anti-HCV (B) (C) (F) or HCV RNA (B) (C) (F)		X	X	X	X	X	X	X	X	
Anti-HBs (B) (C) (F)	X	X	X	X	X	X	X	X	X	
HBeAg (if becomeHBsAg+) (B) (C) (F)	X	X	X	X	X	X	X	X	X	

SPECIMEN SUBMISSION (D)										
Serum (10 ml blood in red top tube)	X		X		X		X	X		X
Whole blood (50 ml in EDTA tubes)	X		X				X			X
TREATMENT										
Usual HBV Care (E)	X	X	X	X	X	X	X	X		

NOTE: Forms are found on the protocol abstract page on the SWOG website (www.swog.org). Forms submission guidelines are found in [Section 14.0](#). Click here for [Footnotes](#).

NOTE: Unless indicated otherwise in the protocol, scheduled procedures and assessments (treatment administration, toxicity assessment for continuous treatment, disease assessment, specimen collection and follow-up activities) must follow the established SWOG guidelines as outlined in SWOG Best Practices, <https://www.swog.org/clinical-trials/protocol-workbench>.

FOOTNOTES for Calendar 9.3:

- (A) If total bilirubin > 3 mg/dL, or if ALT > 5x IULN or > 200 U/L, per usual care (see [Section 7.4](#)).
- (B) If hepatitis flare (defined as ALT > 3 x baseline and > 100 U/L) if patient is HBsAg-positive.
- (C) If hepatitis flare (defined as ALT > 3 x baseline and > 100 U/L) in patient with baseline HBsAg-negative
- (D) See [Sections 15.0](#) and [Appendix 18.1](#)
- (E) Treat at discretion of physician. See [Section 7.2ba](#).
- (F) To be ordered the same day (or within 7 days) if hepatitis flare occurs
- (G) If patient initiated anti-viral treatment per protocol.
- (H) See [Section 7.3b](#).

Allowable Windows

All visits & procedures must occur within \pm 2 weeks of target date (based on date of registration), unless otherwise specified.

10.0 CRITERIA FOR EVALUATION AND ENDPOINT ANALYSIS

10.1 Primary Endpoint

a. Adverse liver outcome: Defined as liver-related death or liver failure (ascites, hepatic encephalopathy or impaired hepatic synthetic function defined as total bilirubin ≥ 5 mg/dL or INR ≥ 2.0) not due to disease progression in the liver. Assessment of the primary endpoint will be made by sites and subsequently adjudicated by the research oversight team by blinded review (see [Appendix 18.4](#)).

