7.1 General Treatment Information

a. Concomitant Medications

Concomitant medications must be assessed prior to initiation of antiviral therapy in Arm 1 (prophylaxis) or if initiated if HBV reactivation occurs (upon indication) in Arms 2 and 3.

Refer to the current FDA-approved package insert for the most comprehensive and up to date information on concomitant medications.

TAF: Concomitant administration of oxcarbazepine, phenobarbital, phenytoin, rifabutin, rifampin, rifapentine, or St. John's Wort is not recommended. If co-administered with carbamazepine, TAF dose should be increased to two tablets once daily. Alternatively, if the above medications cannot be stopped, then study patients may take TDF or ETV.

TDF: none

ETV: none

If possible, avoid use of warfarin. If medically necessary, warfarin may be used during protocol participation after enrollment. For patients who need to take warfarin, monitor INR per [Section 9](#). If the patient has an INR increase, the treating investigator should review to determine if the cause is due to warfarin, study treatment, or acute liver injury. If INR increase is due to acute liver injury, and the increased INR is accompanied by AST, ALT, and bilirubin increase, evaluate the cause per [Section 9](#). Document this determination in the patient's chart.

b. Guidance for Offsite and Virtual Options during the Conduct of the Trial

1. **Laboratory assessments and specimen collections**: All laboratory assessments and specimen collections must be completed at protocol-specified timepoints (see [Section 9.0](#)).
2. **Conducting labs at an offsite facility**: In order to provide participating sites flexibility in treating patients, it is the intent of the **S1614** protocol to

allow for laboratory assessments to be drawn and resulted by local healthcare providers (with appropriate oversight by the Responsible Investigator [local treating investigator]), where administration of the assessment at an off-site facility is in the best interest of the patient and provides for continuity of patient care. Utilization of offsite / local healthcare resources for conduct of patient's laboratory assessments must be documented including procedures for oversight (by the Responsible Investigator) of assessments performed offsite.

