7.4 HBV Monitoring and Adverse Liver Outcomes

During anti-cancer therapy and for 24 months from initial registration, all patients will undergo monitoring for HBV reactivation and adverse liver outcomes (see [Section 10.0](#)). Patients will have ALT and total bilirubin assessed every 4 weeks (\pm 2 weeks) for the first 24 weeks, then every 8 weeks thereafter. Per usual care, if total bilirubin > 3 mg/dL or if ALT > 5x IULN or > 200 U/L then INR will be assessed.

As part of adverse liver outcome assessment, if a hepatitis flare occurs (defined as ALT > 3 x baseline and > 100 U/L) the following labs should be ordered on the same day as the flare or within 7 days of the flare:

- direct bilirubin,
- HBV DNA,
- IgM anti-HAV, and
- either anti-HCV or HCV RNA.

- Patients on Arms 1, and 2 must have HBeAg tested. HBV test results must be reported on the **S1614** Laboratory Values Form.
- If Patients on Arms 3 and 4 become HBsAg positive and have a hepatitis flare, HBeAg testing is required. HBV test results must be reported on the **S1614** Laboratory Values Form.

Additionally, for all HBsAg+ patients, it is recommended that the treating investigator contact [name], M.D., [name], M.D., or [name] at [contact] for evaluation during the study treatment and after discontinuation of study treatment to ensure continued monitoring and to determine whether antiviral therapy should be maintained after discontinuation of study treatment.

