10.2 Other Endpoints

a. HBV reactivation is defined as one of the following:

- ≥ 2 log (100-fold) increase in HBV DNA compared to baseline in patients with detectable HBV DNA at baseline, or
- HBV DNA ≥ 3 log (1,000) IU/mL in a patient with previously undetectable HBV DNA, or
- HBV DNA ≥ 4 log (10,000) IU/mL if baseline HBV DNA not available, or
- HBsAg seroreversion (HBsAg- to HBsAg+) in a patient previously HBsAg-.

b. Hepatitis flare: Hepatitis flare is defined as ALT $> 3 \times$ baseline and >100 U/L.

c. Upon indication: On Arms 2 and 3, anti-HBV therapy is initiated only when HBV reactivation occurs (see [Section 10.2a](#)). Once started, anti-HBV therapy continues for a minimum of 6 months after discontinuation of all anti-cancer therapy or for up to 24 months after registration, whichever comes first (see [Section 7.6](#)).

d. Cancer therapy interruption is defined as dose reduction, treatment delay, or termination of anti-cancer therapy due to hepatic-related reasons other than disease progression in the liver.

e. Death due to any cause measured from date of randomization to date of death.

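### Does the primary endpoint need a written hepatic-cause rule for ascites, bilirubin and INR?

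*Combined protocol and SAP*

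**What the plan says.** Section 10.1 makes the primary endpoint liver-related death or liver failure. Liver failure covers hepatic encephalopathy, ascites and a third form: "impaired hepatic synthetic function defined as total bilirubin ≥ 5 mg/dL or INR ≥ 2.0) not due to disease progression in the liver". Sites assess the event, and it is "subsequently adjudicated by the research oversight team by blinded review". Section 11.1 bases the primary analysis on that central review. Appendix 18.5 gives the reviewers the chart information bearing on the endpoint, with treatment assignment removed.

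Four other places bear on cause:

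- Section 5.2h excludes warfarin at entry, but Section 7.1a says "If medically necessary, warfarin may be used during protocol participation after enrollment". When INR rises, the investigator must "determine if the cause is due to warfarin, study treatment, or acute liver injury" and record the answer in the chart.
- Section 7.4 lists cause-finding tests with the trigger "As part of adverse liver outcome assessment, if a hepatitis flare occurs".
- Section 10.2d limits cancer therapy interruption to events "due to hepatic-related reasons other than disease progression in the liver".
- Section 14.4f asks sites for source documents supporting the diagnosis and for the type of documentation. It does not ask for the cause.

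**The concern.** Section 10.1 gives numerical thresholds and one exclusion. Ascites carries no cause qualifier, and no sentence says that a bilirubin or INR value must come from the liver. The 10.2d definition does carry an attribution test, so its absence from the primary endpoint looks like an oversight. The 7.1a determination is made and filed, but nothing in Sections 10.1, 14.4f or Appendix 18.5 says that it settles endpoint status.

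What is at stake is power. Only about 20 primary events per cohort are expected. Events that no antiviral strategy can prevent, arising equally in both arms, pull the hazard ratio toward 1. They do not raise the false-positive rate.

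**Working it through.** **1. The plan's own figure.** Inputs from Section 11.1: 10% one-year control rate, hazard ratio 0.30, competing death hazard 0.223 per year, n=200 (100 per arm), one-sided alpha 0.05, and 0.045 at the final analysis. Section 7.8 gives 24 months of follow-up.

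- Control hazard: −ln(0.9) = 0.1054. Experimental hazard: 0.3 × 0.1054 = 0.0316, a one-year rate of 1 − exp(−0.0316) = 3.1%, as the plan states.
- Expected events per arm: 100 × λ/(λ+0.223) × [1 − exp(−2(λ+0.223))]. This gives 15.4 and 5.0, total D = 20.4.
- Freedman power: Φ(√D × (1−HR)/(1+HR) − z). At alpha 0.05: Φ(4.517 × 0.7/1.3 − 1.645) = 78.4%. At alpha 0.045 (z = 1.695): 76.9%.
- The Schoenfeld form gives 85.9% and 84.7%. The stated 80% lies between the two methods at alpha 0.05.

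**2. The wording.** The laboratory limits define impaired *hepatic* synthetic function. That is one form of *liver* failure, which in turn is an adverse *liver* outcome. A warfarin INR or peritoneal ascites is none of these in ordinary use. The contrast with 10.2d is weaker than it looks: a treatment interruption is not hepatic by nature, so it needs the qualifier, whereas liver failure already contains it.

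**3. The routes.** Entry excludes warfarin (5.2h), Stage IV disease (5.1a), and known cirrhosis or malignancy involving the liver (5.1c). On-study INR in the Section 9 calendars carries a footnote tying it to bilirubin > 3 mg/dL, or ALT > 5 times the institutional upper limit or > 200 U/L. An isolated warfarin INR is therefore not clearly a scheduled measurement, though usual-care values can reach the chart. Direct bilirubin carries the same footnote, so a bilirubin of 5 mg/dL calls for it without a flare, although it does not settle cause alone.

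**4. Size, if reviewers did accept such events.** The documents give no rate. Assume a non-hepatic hazard q of 0.005 or 0.01 per year in each arm, and a share f accepted at review. Freedman, alpha 0.045; differences are taken before rounding.

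*On top of the 10%:* hazards 0.1054 + fq and 0.0316 + fq.

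| q | f | HR | Power | Loss from 76.9% (points) |
|---|---|---|---|---|
| 0.005 | 25% | 0.308 | 76.2% | 0.7 |
| 0.005 | 50% | 0.316 | 75.5% | 1.4 |
| 0.005 | 100% | 0.332 | 74.2% | 2.8 |
| 0.01 | 25% | 0.316 | 75.5% | 1.4 |
| 0.01 | 50% | 0.332 | 74.2% | 2.8 |
| 0.01 | 100% | 0.361 | 71.5% | 5.4 |

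Full acceptance corresponds to about 1.5 (q = 0.005) or 3.0 (q = 0.01) such events per cohort.

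*Inside the 10%:* hazards (0.1054 − q) + fq and 0.3(0.1054 − q) + fq. With a perfect rule (f = 0), power is 75.3% (q = 0.005) or 73.5% (q = 0.01). Without it, at f = 25/50/100%, power is 74.5/73.8/72.3% or 71.9/70.4/67.5%. The rule would recover 0.7/1.5/2.9 or 1.6/3.1/6.0 points.

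**5. Cost of a rule.** If a rule led reviewers to reject a share m of true hepatic events in both arms, both hazards scale by (1 − m). At m = 2, 5 and 10%, power is 76.2, 75.2 and 73.3%. With events on top, the gain is cancelled at m = 2.0/4.0/7.7% (q = 0.005; f = 25/50/100%) or 4.0/7.7/14.3% (q = 0.01). In the mildest case that is 0.02 × 20.4, or about 0.4 of an event.

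**6. The cross-reference.** Section 10.1 cites Appendix 18.4 for the blinded review. That appendix is the Intake Calendar, and the review is in 18.5. The same one-place shift affects viral status (5.3a cites 18.2, correct 18.3), the Intake Calendar (7.5 cites 18.3, correct 18.4) and the antiviral table (7.3b cites 18.5, correct 18.6). This is renumbering, with no analytic consequence.

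**The case for a change.** The best case for a change is that reviewer judgement is less secure than it sounds. Appendix 18.5 names the reviewers and their materials but gives no decision criteria. Most cause tests in Section 7.4 depend on an ALT flare, so ascites without one may arrive with little evidence of cause. The review takes place when follow-up is complete, whereas the interim efficacy look and the monitoring of the standard-arm event rate (11.3) come earlier and, on that timing, rest on site classification. Two sentences and a cause field would cost little.

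The textual part stands: no written rule links cause to endpoint status. The timing point also stands as a fact, but a few non-preventable events, equal in both arms, make the 0.005 interim boundary harder to cross. At an assumed 0.5–1% per year against 10%, they would hardly alter a judgement about extending accrual. For the primary analysis, settling disagreement between sites is the purpose of central review by one team. Whether the site forms already hold a cause field cannot be checked, because the forms are not in the documents.

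The remedy has its own drawback. Making the 7.1a determination decisive would let the treating investigator, who knows the arm, settle part of an endpoint meant to be judged blind. It is better as one item in the chart, which is how reviewers can already use it. A rule would also leave liver injury from anti-cancer drugs in the endpoint, so that dilution would remain.

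**Conclusion.** No change to the plan is needed. Section 10.1 leaves hepatic attribution to be read from the terms it uses, and blinded reviewers with the relevant chart can be expected to apply it. A clarifying sentence would be optional.

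Any loss is hypothetical: 0 to about 5 points of power with such events on top of the 10% rate, or up to about 6 recoverable points if they lie inside it. These figures rest on an assumed 0.5–1% yearly rate, an assumed acceptance share, equal occurrence in both arms, full 24-month follow-up and the Freedman approximation. The 100% acceptance figures are upper bounds. There is no bias toward a false positive. The appendix number in Section 10.1 is a clerical slip to correct whenever the text is next revised.
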